symptomatic improvement by lower extremity venous Doppler ultrasonography at 6 and 12 weeks post-treatment follow-up. Patients with Varicose Vein of Lower Extremity Prolonged venous reflux time (superficial vein ≥ 0.5 sec, deep vein ≥ 1 sec) (N=200) Randomization Vitis Vinifera Extract (Entelon®) + Therapeutic lifestyle changes only Therapeutic lifestyle changes (N=100)(N=100)Primary endpoint: Change in venous reflux time from baseline to 6, 12 weeks Secondary endpoint: improvement of venous veflux (superficial vein < 0.5 sec, deep vein < 1 sec) Change from baseline to 6, 12 weeks in vessel diameter, venous reflux volume, clinical status by VCCS, CIVIQ-14 Inclusion 1) Adult males and females aged between 19- and under 80-years-old 2) Patients with the following findings on venous Doppler ultrasound criteria examination: - Superficial veins (such as the great saphenous vein, small saphenous vein, etc.) showing venous reflux for 0.5 seconds or longer - Deep veins (such as the femoral vein, etc.) showing venous reflux for 1 second or longer 3) Patients who have completed the washout period as described below by Visit 2, including the screening period: - Analgesics, steroids, anti-inflammatory drugs, and venoactive medications (such as Entelon®, etc.): at least 4 weeks 4) Patients who voluntarily provide written informed consent to participate in this clinical trial **Exclusion** 1) Peripheral arterial occlusive disease in the lower limbs criteria 2) Asymptomatic lower extremity varicose veins 3) Acute deep vein thrombosis 4) Frequent lower limb pain due to neuropathy 5) Patients who have undergone or are scheduled for varicose vein procedures/surgeries (However, patients who have undergone a procedure or surgery more than 1 year prior to the screening date are eligible to participate.) 6) Patients diagnosed with systemic diseases causing edema or thrombosis, heart failure. endocrine diseases such as (hypothyroidism, Cushing's syndrome, uncontrolled diabetes), allergic reactions to medications, urticaria and angioedema,

malabsorption and protein-calorie malnutrition, obstructive sleep apnea, or thrombophilia, as determined by the investigator

- A. History of malignancy within the past 5 years, but the following cases are eligible for clinical trial participation:
- B. Those who have a history within the past 5 years but maintain a cured state without recurrence or metastasis
- C. Those who have completed treatment for their tumor and have been disease-free for at least 5 years from the screening date
- 7) Those who have passed at least 1 year since the screening date after complete resection of basal cell carcinoma/squamous cell carcinoma, radical resection of thyroid papillary cancer, or successful treatment of cervical intraepithelial neoplasia
- 8) Severe renal dysfunction (serum creatinine levels more than twice the normal upper limit of the institution) on the screening date
- 9) Severe liver dysfunction (ALT or AST levels more than three times the normal upper limit of the institution) on the screening date
- 10) Need to receive diuretics or contraindicated medications and therapies that may affect the results of this clinical trial during the study period (However, patients who have been taking antihypertensive medications (calcium channel blockers, betablockers, angiotensin-converting enzyme inhibitors, vasodilators, vasoconstrictors) at the same dosage for at least 4 weeks (28 days) before screening and will maintain the same dosage and administration during the study period are eligible to participate)
- 11) History of clinically significant psychiatric disorders or alcohol abuse
- 12) History of hypersensitivity reactions to the investigational drug or its ingredients
- 13) Those who have participated in or are scheduled to participate in other clinical trials (investigational drugs, medical devices, health functional foods) within 12 weeks of the screening date
- 14) Pregnant or breastfeeding women
- 15) Women of childbearing potential who plan to become pregnant during the clinical trial participation period
- 16) Individuals deemed unsuitable for participation in the clinical trial by the investigator

# Primary endpoint

Change in venous reflux time [Time Frame: 6, 12 weeks]

- We will assess the changes in venous reflux time of target vessel using lower limb venous Doppler ultrasound examinations.

# Secondary endpoint

- 1) Improvement of venous reflux [Time Frame: 6, 12 weeks]
- We will assess the improvement of venous reflux of target vessel (superficial vein < 0.5 seconds, deep vein < 1 seconds)
- 2) Change in varicose vein size area [Time Frame: 6, 12 weeks]
- We will assess the changes in varicose vein diameter of target vessel using lower limb venous Doppler ultrasound examinations.
- 3) Change in venous reflux volume [Time Frame: 6, 12 weeks]
- We will assess the changes in venous reflux volume of target vessel using the Venous Doppler Reflux VTI x varicose vein size area.
- 4) Change of extracellular water ratio [Time Frame: 6, 12 weeks]
- We will assess the changes in extracellular water (ECW) ratio (ECW/total body water) of target limb using body composition analyzer (ACCUNIQ BC720®).
- 5) Improvement in VCSS [Time Frame: 6, 12 weeks]
- The Venous Clinical Severity Score (VCSS) is a clinical measure that assesses the severity of chronic venous diseases. The score ranges from 0 (indicating no symptoms) to 30 (indicating severe venous disease). The scoring system takes into account various factors including pain; varicose veins; venous edema; skin pigmentation; inflammation; induration; and active ulcers and their duration, size, and number. A higher score on the VCSS indicates a worse outcome, implying a more severe state of venous disease.
- 6) Improvement of CIVIQ-14 [Time Frame: 6, 12 weeks]
- The Chronic Venous Insufficiency Quality of Life Questionnaire (CIVIQ-14) is a valuable tool designed to evaluate the impact of chronic venous insufficiency on a patient's quality of life. The 'improvement' in CIVIQ-14 refers to the enhancement in scores, indicating better management of symptoms, greater comfort, and overall wellbeing of the patient over the course of treatment or intervention.

#### Sample size

#### 200 patients

# Sample size calculation

This study is an exploratory study to determine the effectiveness of venous reflux improvement after medication in patients with varicose veins, and there are limited prior studies to draw upon. Therefore, the study design is subject to a number of assumptions. In addition, it is not advisable to apply the same process for calculating the number of patients to meet the mathematical basis for a confirmatory study as for a confirmatory study when controlling for type 1 and type 2 errors.

Nevertheless, a few assumptions can be made to develop a power calculation process that is similar to that of a confirmatory study. According to the literature, the duration of reflux was measured slightly differently at each point, and we would like to calculate the number of

patients based on GSV, prox, which had the largest number of patients (Reference: J Vasc Surg. 2004 Aug;40(2):303-10.). In this study, we would like to conduct an analysis on the difference between the means, but no relevant evidence was found; therefore, we borrowed the median value of the references as the mean. This assumes that the number of n is large enough (174) according to the principle of central limit theorem, such that the gap between the median and the mean is not large. We also calculated the standard deviation using the range and the number of n. By calculating the standard deviation of other parameters together, we found that the standard deviation of the valve-carrying segments can be assumed as approximately 1.8 overall. The results of the drug group are expected to improve by about 10% to 15%, and we decided to conservatively assume an improvement of 12.5% to calculate the number of patients.

Valve-carrying	n	Median (s)	Range (s)
segment			
GSV, prox	174	6.1	0.7-10.0
GSV, dist	84	3.5	0.7-10.0
SSV	91	4.6	0.6-10.0

In this case, assuming a normal distribution and based on a Z-test with the same variance in both groups, the following calculation result was obtained under  $\alpha$ =0.025,  $\beta$ =0.2. The calculation was performed using PASS15. A one-tailed test will be performed to determine superiority if the difference between the drug and lifestyle treatment groups is less than zero. Assuming that patients may drop out during the study, the dropout rate was set at 20% to account for dropout in a typical clinical setting. Therefore, the total number of patients was calculated to be 160, with 80 patients in each group, and considering the dropout rate of 20%, we plan to recruit 200 patients, 100 in each group, to conduct the study.

		Two-S	Sample Z-	Tests Assun	ning Equal	Variance		
Numeric Results for Two-Sample Z-Test Assuming Equal Variance Alternative Hypothesis: H1: δ = μ1 - μ2 < 0								
		11. 0 – μ1 -	μ2 < 0					
Target	Actual	N/4	NO		4		-	- 41-1-
Power	Power	N1	N2	N 460	μ1	μ2	δ	σAlpha
0.80	0.80260	80	80	160	5.3	6.1	-0.8	1.8 0.025
Group sar means wh deviation t	r Statements imple sizes of 80 ien the populati for both groups two-sample ed	ion mean d of 1.8 and	ifference is with a sigr	s μ1 - μ2 = 5.:	3 - 6.1 = -0.8	3 with a st	andard .	
Group sar means wh deviation to one-sided	nple sizes of 80 en the populat for both groups two-sample ed	ion mean d of 1.8 and l ual-variand	ifference is with a sigr	s μ1 - μ2 = 5.:	3 - 6.1 = -0.8	3 with a st	andard .	
Group sar means wh deviation t one-sided	nple sizes of 80 en the populat for both groups	ion mean d of 1.8 and l ual-variand	ifference is with a sigr	s μ1 - μ2 = 5.:	3 - 6.1 = -0.8 I (alpha) of 0	3 with a st 0.025 usin	andard .	
Group sar means wh deviation to one-sided	nple sizes of 80 en the populat for both groups two-sample ed	ion mean d of 1.8 and l ual-variand	ifference is with a sigr	s μ1 - μ2 = 5.:	3 - 6.1 = -0.8 I (alpha) of (	3 with a st	andard g a	
Group sar means wh deviation to one-sided	nple sizes of 80 en the populat for both groups two-sample ed	ion mean d of 1.8 and jual-variand e Size	ifference is with a sigr	s µ1 - µ2 = 5.: nificance leve	3 - 6.1 = -0.8 I (alpha) of ( [ [ E	3 with a st 0.025 usin 0ropout-	andard g a	
Group sar means wh deviation to one-sided Dropout-I	nple sizes of 80 een the populat for both groups two-sample ec	ion mean d of 1.8 and jual-variand e Size	ifference is with a sigr ce z-test.	s µ1 - µ2 = 5.: nificance leve	3 - 6.1 = -0.8 I (alpha) of ( [ [ E	3 with a st 0.025 usin Oropout- nrollment	andard g a	
Group sar means wh deviation t one-sided	nple sizes of 80 een the populat for both groups two-sample ec	ion mean d of 1.8 and jual-variand e Size	ifference is with a sigr ce z-test.	s µ1 - µ2 = 5.: nificance leve	3 - 6.1 = -0.8 I (alpha) of ( [ [ E	3 with a st 0.025 usin Oropout- nrollment	andard g a	

Study period	2023.07.01 ~ 2024.12.31			
	Patient enrollment: IRB approval date ~2024.04.31			
	End of follow-up period: 2024.07.31			
	Analysis and report: ~2024.12.31			
Funding	Hanlim pharm.CO.LTD.			
Agency				

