## 11. Data Analysis & Statistical Considerations

#### 11.1. Sample size calculation

This is an exploratory study to determine the effectiveness of medication in improving venous reflux in patients with varicose veins, and there are limited prior studies to draw upon. Therefore, the study design is based on some assumptions, and it is not advisable to apply the same process to calculate the number of participants that are required to meet the mathematical basis for a confirmatory study when controlling for type 1 and type 2 errors.

Nevertheless, a few assumptions can be made to develop a power-calculation process similar to that of a confirmatory study. According to the literature, the duration of reflux was measured slightly differently at each point, and we calculated the number of participants based on the GSV, prox, which had the largest number of patients (Reference: J Vasc Surg. 2004 Aug;40(2):303-10.). In this study, we examined the difference between the means, but we could not find any evidence; therefore, we used the median value of the references as the mean. This assumes that n is sufficiently large (174), according to the principle of the central limit theorem, so the gap between the median and mean is not large. We also calculated the standard deviation using the range and number of n. By calculating the standard deviations of the other parameters together, we found that the standard deviation of the valve-carrying segments can be assumed to be approximately 1.8 overall. The results of the drug group are expected to improve by approximately 10% to 15%; therefore, we decided to conservatively assume an improvement of 12.5% to calculate the number of participants.

Valve-carrying	n	Median (s)	Range (s)	sd
segment				
GSV, prox	174	6.1	0.7-10.0	1.737
GSV, dist	84	3.5	0.7-10.0	1.921
SSV	91	4.6	0.6-10.0	1.918

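### The 6.1 s planning mean is a published median justified by a theorem that does not apply, and even at 6.1 s the stated 12.5% effect gives 76% power, not the printed 80%

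*Combined protocol and SAP*

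**What the plan says.** Sample size is set out in section 1 (Research summary, Sample size calculation) and repeated in section 11.1. The authors wanted a mean reflux time for the proximal great saphenous vein, found none, and so "we borrowed the median value of the references as the mean". The source row has n = 174, median 6.1 s and range 0.7 to 10.0 s. Section 1 defends the substitution in these terms: "This assumes that the number of n is large enough (174) according to the principle of central limit theorem, such that the gap" separating the two figures is taken to be small. Section 11.1 gives the same defence: "This assumes that n is sufficiently large (174), according to the principle of the central limit theorem".

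The effect is set as a percentage. From an expected 10% to 15%, "we decided to conservatively assume an improvement of 12.5% to calculate the number of patients". On spread, the "standard deviation of the valve-carrying segments can be assumed as approximately 1.8 overall". The calculation proceeds "assuming a normal distribution and based on a Z-test with the same variance in both groups", one-sided at 0.025. The PASS output in section 1 compares means of 5.3 and 6.1 s (difference -0.8 s) and prints a power of 0.80260. Accordingly, "the total number of patients was calculated to be 160, with 80 patients in each group", raised to 200 for 20% dropout.

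Both sections call the study exploratory and say its design rests on assumptions. Neither gives a mean, a distribution shape or a sensitivity analysis for the planning mean.

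**The concern.** Two things do not follow.

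First, a large n makes the sample mean approximately normal and the sample median precise. It does not draw the two together: in a skewed population the gap stays where it is however many patients are measured. The reason given for using 6.1 s as a mean is therefore not a reason, and the documents offer no other.

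Second, the effect is stated as 12.5% but the figure entered is larger than 12.5% of 6.1 s.

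Because the effect is a percentage of the planning mean, the target in seconds scales with that mean, and so does the power. The 80% is what a reader will use to judge a null result, so it should match the effect the text says was assumed.

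**Working it through.** **Inputs from sections 1 and 11.1:** control mean 6.1 s; effect 12.5%; entered difference 0.8 s; SD 1.8 s; 80 per arm; one-sided alpha 0.025; dropout 20%.

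**Formula:** power = Φ(δ / SE − 1.960), with SE = 1.8 × √(2/80) = 0.2846 s.

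**1. The plan's own figure.** δ = 0.8: 0.8/0.2846 = 2.811, and Φ(0.851) = 0.8026. Required n = 2 × (1.960 + 0.842)² × 1.8² / 0.8² = 79.5, so 80 per arm; 80/0.8 = 100 per arm. Both reproduce exactly. The match also shows that 0.8 s itself was used, and is not just a rounded display of 0.7625 s.

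**2. The stated effect at the stated mean.** 0.125 × 6.1 = 0.7625 s, a treated mean of 5.3375 s against the 5.3 s entered. The entered 0.8 s is 0.8/6.1 = 13.1%. Power: 0.7625/0.2846 = 2.679, and Φ(0.719) = 0.764. Reaching 80% at 0.7625 s would need 88 per arm, or 220 enrolled.

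**3. Does n close the gap between median and mean?** In simulated samples from an exponential population (SD 1), the average gap was 0.302 at n = 174, 0.307 at n = 2,000 and 0.307 at n = 200,000. It does not shrink.

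**4. Is symmetry suggested by the plan's table?** No. The proximal median (6.1 s) lies above its range midpoint, (0.7 + 10.0)/2 = 5.35 s. The distal median (3.5 s), on the same range, lies well below it.

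**5. Sensitivity to the mean.** SD 1.8 s and 80 per arm are held fixed, with δ = 12.5% of the mean. All means other than 6.1 s are assumptions.

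| Mean (s) | Basis | δ (s) | Power |
|---|---|---|---|
| 5.725 | (0.7 + 2 × 6.1 + 10.0)/4 | 0.716 | 71.0% |
| 6.01 | beta shape on 0.7–10.0, median 6.1, SD 1.8 | 0.751 | 75.2% |
| 6.1 | as planned | 0.7625 | 76.4% |
| 6.4 | 0.8/0.125 | 0.800 | 80.3% |
| 7.0 | illustrative | 0.875 | 86.8% |

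**6. Separating the two effects.** The drop from 80.3% to 76.4% has nothing to do with median versus mean; it comes from entering 0.8 s for 0.7625 s. The substitution accounts for about 1 point (76.4% to 75.2%) under the beta shape or about 5 points (76.4% to 71.0%) under the range-based conversion. It is a gain if the mean exceeds 6.1 s.

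**The case against.** The strongest reply is that nothing is hidden. The sentence opens as an assumption, the text admits that no evidence on means was found, and the study is labelled exploratory. The printed alternative is 5.3 against 6.1 s with SD 1.8 s, and for a 0.8 s difference the power is correct whatever the control mean is. All of this stands. What it does not rescue is the rationale, which is wrong in both sections, or the mismatch between 12.5% in the text and 13.1% in the calculation.

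It is also fair that the 5.725 s conversion puts half its weight on two extreme observations, and that the two conversions disagree. Neither should be treated as the true mean.

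A reader might infer three stronger things.

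- **That the substitution leaves the trial underpowered.** The documents do not show this. The mean could lie above 6.1 s, and at 6.4 s a 12.5% effect has 80.3% power.
- **That the 12.5% itself rests on 6.1 s.** It does not. It is a separate assumption; only its translation into seconds uses 6.1 s.
- **That power could be anywhere from 47% to 93%.** Those figures come from means of 4.3 and 7.9 s, one full SD from the median. A gap that large needs an essentially two-point distribution, which does not fit the reported range. The outer limit of 3.4 s implied by median and range alone is worse: it needs half the values at 0.7 s and half at 6.1 s, an SD of (6.1 − 0.7)/2 = 2.7 s, not 1.8 s.

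**Conclusion.** The point holds as a fault in justification and in reported power, not in the PASS arithmetic. The theorem gives no support for treating a median of 6.1 s as a mean, so the 0.8 s difference and the stated power rest on an unsupported input whose error has unknown direction and size. Under the two conversions tried, the effect on power is a loss of 1 to 5 points.

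The firmer finding needs no view on the mean: at the plan's own 6.1 s, a 12.5% effect gives 76.4% power, not 80.26%. This takes SD 1.8 s as given. With the 1.737 s that section 11.1 lists for the proximal segment it would be 79.3%, and with the 1.921 s listed for the distal segment 70.9%. The matter is worth correcting but does not threaten the design.

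**What to change.** In sections 1 and 11.1, delete the central limit theorem sentence and say plainly that 6.1 s is a published median assumed to serve as the mean. Then take one of two routes:

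- **Absolute target.** Define the planned difference as 0.8 s, noting that it is 13.1% of 6.1 s. The 80% power then stands as printed.
- **Percentage target.** Keep 12.5%, restate power as about 76% with 80 per arm, and show sensitivity on both sides of 6.1 s: about 71% at 5.7 s, 76% at 6.1 s and 80% at 6.4 s.

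N stays at 200 and conduct is unchanged. The cost is a few sentences and, on the second route, a less favourable stated power.

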#### 2. Introduction

Varicose veins arise from a malfunction in the valves within the veins of the legs, which allows blood to be transported to the heart to flow backward into the lower extremities. This backflow results in pooling of blood in these areas, which subsequently triggers various symptoms. Typically, malfunction occurs in valves that are located in superficial veins, such as the great saphenous vein, which drains into the deep vein at the groin, the small saphenous vein at the calf, or perforating veins. This malfunction allows blood reflux, causing the veins in the calf to dilate. The primary cause is incompetence of the leg vein valves.

According to an analysis of varicose vein treatment data from 2016 to 2020, the number of treated patients increased by 50,000 from 162,000 in 2016 to 212,000 in 2020. This represents an average annual increase of 7%. With an aging population, the number of patients with varicose veins is expected to continue to rise. Varicose veins frequently occur and worsen in older individuals, women, those who have given birth, obese individuals, and those with jobs that require long periods of standing. If left untreated, varicose veins resulting from valve incompetence can worsen, leading to complications, such as skin pigmentation, swelling, and leg ulcers. Therefore, treatment is essential, particularly for patients with risk factors, and prevention is of paramount importance.

Patients typically visit clinics because of enlarged veins in the calf. However, various symptoms can occur when accompanied by valve incompetence. These include aches, spasms, fatigue, dull pain, night pain, heat sensations, and feelings of heaviness in the legs. It is also possible that musculoskeletal, neurological, or arterial issues trigger these symptoms, necessitating specialist consultations. Valve incompetence is crucial in cases of suspected varicose veins. Typically, Doppler ultrasonography is used to confirm reflux in the superficial veins (great and small saphenous veins) and deep veins (popliteal veins). If dilation of the branch veins is noted, a diagnosis is made and the treatment approach is determined. Even if symptoms are present in only one leg, an ultrasound examination is conducted on both sides. Treatment of varicose veins can generally be divided into conservative and invasive procedures. Conservative treatment involves lifestyle modifications and the use of compression stockings. Surgical treatment may be required if these measures are ineffective or if they interfere with daily life. By removing or ablating the refluxing superficial veins using high-frequency radio waves or lasers, blood flow can be stopped, thereby relieving the symptoms. However, most of these treatments are not covered by insurance and can be relatively expensive, potentially

placing a significant financial burden on patients. Furthermore, because deep veins are responsible for 90% of blood transport, surgical treatment may not be possible, leaving only conservative treatment as an option.

Entelon®, a pharmaceutical that is derived from Vitis vinifera seeds, is used for non-invasive treatment of various conditions. The primary goal of this treatment is to improve symptoms related to veno-lymphatic insufficiency, such as feelings of heaviness in the legs, pain, and restless legs syndrome. Enteron is composed of Vitis vinifera seed (grape seed) extract, which is a natural compound. It strengthens the vascular wall by protecting collagen and elastin, improving their structure, and increasing fibronectin and elastonectin, which promote extracellular matrix binding. It also selectively binds to GAGs, promotes their synthesis, and inhibits their breakdown and trypsin activity. Additionally, grape seed extract protects vascular wall components (antioxidant action of Vit.C 50 times, Vit.E 20 times) and inhibits cholesterol accumulation. Since its launch in 1998, Enteron® has been used to treat symptoms such as heaviness, pain, and discomfort in the legs, lymphedema resulting from breast cancer treatment, and non-proliferative diabetic retinopathy. Its safety has been established since its release, and it has been shown to reduce leg volume compared to placebo in patients with leg swelling (Sano A, Tokutake S, Seo A. Proanthocyanidin-rich grape seed extract reduces leg swelling in healthy women during prolonged sitting. J Sci Food Agric. 2013 Feb;93(3):457-62.). However, the relationship between the degree of venous reflux and associated symptoms in patients with varicose veins is not well understood. Furthermore, there is a lack of research on whether the administration of Entelon® improves venous reflux in patients with varicose veins.

In this study, we aim to confirm the improvement of venous reflux through follow-up Doppler ultrasound examinations in patients with varicose veins who have been prescribed Enteron® along with therapeutic lifestyle changes.

